6.1.2.7 Responsibilities of the Sponsor

The Sponsor is responsible for fulfilling all obligations regarding notification of Regulatory Authorities and IECs/IRBs according to applicable regulatory requirements (eg, expedited and periodic reporting, serious unexpected suspected adverse reactions, Development Safety Update Report). In addition, the Sponsor will provide safety information to Investigators according to the current regulations.

6.1.3 Laboratory Parameters

Laboratory assessments will be performed by a central laboratory, as identified in the List of Study Personnel ([Appendix 1](#)) at the time points outlined in [Appendix 2](#).

The tests listed in [Table 6.1](#) will be conducted on samples collected and analysed by standard laboratory procedures at the time points outlined on the Schedule of Assessments ([Appendix 2](#)). Blood draws that are not done must be reported as such on the eCRFs.

Table 6.1: Laboratory Parameters

Haematology		
Haemoglobin	White blood cell count with differential(neutrophils,neutrophil bands, lymphocytes, monocytes, eosinophils, basophils)	Mean corpuscular volume
Haematocrit		Mean corpuscular haemoglobin concentration
Red blood cell count		Red cell morphology
Platelets		
Chemistry		
Alkaline phosphatase	Total protein	Creatinine
Alanine aminotransferase	Blood urea nitrogen	Gamma glutamyl transpeptidase
Aspartate aminotransferase	Albumin	Electrolytes (sodium, potassium, chloride)
Total bilirubin	Glucose ^a	Cholesterol (total, HDL, LDL)
Urine ^b		
Appearance	Glucose	Occult blood
Specific gravity	Ketones	
pH		Macroscopic haematuria
Other Tests		
Pregnancy tests for women of childbearing potential: Serum at Screening (Visit 1), the ET Visit (if the subject is discontinuing from the study), or the End of Study Visit (Visit 7) and urine (at all other visits)		

AE = adverse event; ET = early termination; HDL = high-density lipoprotein; LDL = low-density lipoprotein

- a Glucose should be measured fasting. If for any reason a subject is not able to follow this recommendation, then there should be a 2-hour gap between a meal and the blood sample.
- b Microscopic evaluations will be performed if dipstick is positive. At Screening, if dipstick is positive and microscopic evaluation is abnormal, the subject must be excluded from participating in the study. If during the study, the dipstick is positive and the microscopic evaluation is abnormal these results will be recorded as an AE with the follow-up of the AE reported to the Medical Monitor.

6.1.4 Vital Signs

Vital signs will be measured and recorded at the time points outlined on the Schedule of Assessments ([Appendix 2](#)). The following measurements must be performed: systolic/diastolic blood pressure, heart rate, and body temperature. Vital signs will be measured after the subject has been in the supine position for at least 5 minutes. At the Randomization Visit (Visit 3), vital signs will be measured 3 times in order to determine the mean blood pressure. All measurements will be recorded on the vital signs eCRF. Abnormal test results may be repeated at the discretion

of the Investigator and must be reported on the corresponding eCRF. When vital signs and ECGs occur at the same time, vital signs should be performed before ECGs.

6.1.5 Electrocardiograms

During the study, 12-lead ECGs will be performed at the time points designated on the Schedule of Assessments ([Appendix 2](#)).

The subject must be in a supine position in a rested and calm state for at least 5 minutes before ECG assessment is conducted. If the subject is unable to be in the supine position, the subject should be in the most recumbent position possible. All ECGs should be performed in a standardized method, in triplicate, and approximately 30 seconds apart, prior to blood draws or other invasive procedures. Each ECG must include the following measurements: ventricular rate, QRS, QT, corrected QT, RR, and PR intervals.

The Investigator or designated site physician will review and sign all ECGs. Results must be summarized in writing and classified as normal; abnormal; abnormal, clinically relevant; or abnormal, not clinically relevant. Once signed, the original ECG tracing will be retained with the subject's source documents. At the request of the Sponsor, a copy of the original ECG will be made available.

6.1.6 Physical Examinations

The Investigator or qualified designee will perform a complete physical examination at the time points outlined on the Schedule of Assessments ([Appendix 2](#)). Pre-dose abnormal findings will be reported on the medical history eCRF. Any adverse change from the baseline physical examination (Day 0 examination) will be documented on the AE eCRF. Weight will be measured at Screening, at Visit 6 (Eight weeks Postrandomization/ Early Termination Visit) and Visit 7 (Week 15, Post-Treatment Safety Follow-up Visit).

A full physical examination will include examination of general appearance, skin, neck (including thyroid), eyes, ears, nose, throat, heart, lungs, abdomen, lymph nodes, extremities, urinary system, musculoskeletal system, and nervous system, (including the central nervous system).

6.1.7 Prior and Concomitant Medication

Prior and concomitant medication will be recorded at the time points outlined on the Schedule of Assessments ([Appendix 2](#)). All prior and concomitant medications taken by the subject will be recorded in the appropriate eCRF along with dose, dates of administration, and reason for use.

6.1.8 Postvoid Residual Volume

Bladder scans (ultrasound) for postvoid residual volume will be recorded at the time points outlined on the Schedule of Assessments ([Appendix 2](#)). Measurements should be performed within 15 minutes of the void. The time of the bladder scan and the time of the preceding void will also be recorded. Subjects who demonstrate a PVR >150 mL at Screening or at Day 0

(Visit 3), will require a repeat bladder scan. If the PVR is >150 mL, the subject will be ineligible for study.

Catheterization should not be used to capture post void residual volume.

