4.2 Exclusion Criteria

Individuals who meet any of the following criteria are not eligible to participate in the study.

- 1. History of anti-incontinence surgery in past 12 months
- 2. Use of Botox for the treatment of urinary incontinence in the past 12 months
- 3. Current or recent (3 months) use of any pharmacologic agent used to treat symptoms of urinary incontinence
- 4. For women: Grade III/IV pelvic organ prolapse; defined per clinical practice
- 5. For women: History of pelvic prolapse repair or urethral diverticulectomy within 12 months of Screening.
For men: urethral surgery within 6 months of Screening.
- 6. History of interstitial cystitis or bladder-related pain
- 7. Subjects with concurrent (at Screening), recent (within 30 days), chronic, or recurrent (> 4 per year) urinary tract infections (positive dipstick for urinary tract infection and abnormal microscopic evaluation, signs and symptoms) or unevaluated microhematuria
- 8. History of diagnosed gastrointestinal obstructive disorders
- 9. Chronic severe constipation
- 10. History of radiation cystitis or history of pelvic irradiation
- 11. Electrostimulation, biofeedback, or bladder training therapy (behavioural therapy), during the previous month prior to Screening, or the intention to initiate such therapies during the study period. Pessaries and implants are also excluded.
- 12. Postvoid residual (PVR) urine volume > 150 mL
- 13. Diagnosis of dementia
- 14. Diagnosis of epilepsy

15. Diagnosis of acute narrow-angle glaucoma
16. History of mania or diagnosis of bipolar disorder and/or seizures
17. Subjects with uncontrolled hypertension
18. Documented history of myocardial infarction, unstable angina, and/or has undergone coronary artery bypass surgery and/or percutaneous transluminal coronary angioplasty in the past year
19. Congestive heart failure (New York Heart Association Class III or IV heart failure; [Appendix 3](#))
20. Any concurrent condition or any clinically significant abnormality on the Screening physical examination, laboratory tests, electrocardiogram (ECG; including ischemic heart disease), Hepatitis B or C, which, in the opinion of the Investigator, may affect the interpretation of safety or efficacy data, or which otherwise contraindicates participation in a clinical study with litoxetine:
 - a. Hypersensitivity to litoxetine or any of its ingredients
 - b. History of clinically significant drug hypersensitivity

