6.1.2.3 Responsibilities of the Investigator

Adverse event data should be obtained through observation of the subject, from any information volunteered by the subject, or through subject questioning. The general type of question asked could be similar to: "Do you have any health problems?" or "Have you had any health problems since your last clinic visit?"

Specific emphasis should be given to explore the occurrence of psychiatric events (nervousness, anxiety, panic attacks, insomnia, aggression, mania, suicidal ideation, development/worsening of depression). The patient should be routinely monitored by the C-SSRS, BDI-II, BAI and PSQI, as laid out in section 6.1.1.

If any patient experience suggestive suicidal ideation/behaviour as per the C-SSRS s/he will be submitted for psychiatric evaluation. The outcome of the psychiatric evaluation will determine the patient's suicidal state and whether the patient will continue in the study or prematurely withdrawn from participation.

Adverse Event terms such as euphoria, dissociative effects, hallucinosis, psychosis, impaired cognition, attention, mood and psychomotor effects, inappropriate affect, patient dropouts, overdoses, misuse and lost or unaccounted for medication and unjustified dose increases will result in detailed narratives, as they may be indicative of abuse potential.

Adverse events are to be documented/recorded accurately and completely on the AE pages of the respective eCRF and in the subject's source data.

All non-treatment and treatment-emergent AEs will be recorded. This is true even if the study drug was not administered according to study protocol.

For conditions leading to unplanned surgical procedures, the underlying condition, but not the procedure, should be documented as an AE.

Reporting Immediately Reportable Adverse Events (IRAEs):

For AEs that are “serious” (SAEs) additional separate documentation is required using the electronic SAE Forms.

The following variables will be recorded on the electronic SAE Form and on the eCRFs provided in accordance to the eCRF completion guidelines:

- Description of the event, including its duration (date of onset and resolution),
- Whether the event constitutes a SAE or not (if yes, see event seriousness criteria in [Section 6.1.2.1.2](#))
- Any action taken (eg, changes to study treatment, other treatment given, and follow up tests)
- Outcome of the event

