7.1.6 Eight Weeks Post-randomisation/Early Termination Visit – Visit 6 (Day 70)

The following procedures are to be completed during the 8 Weeks Post-randomisation/Early Termination Visit at time points outlined on the Schedule of Assessments ([Appendix 2](#)).

If this is the Early Termination Visit, the Investigator should use every effort to encourage the subject to taper study medication for 1 week and to return for the Safety Follow-up Visit (Visit 7).

- Record current medications
- Measure and record vital signs (blood pressure, heart rate, and body temperature)
- Complete full physical examination (including weight)
- Complete the C-SSRS, BDI-II, BAI, PSQI
- Determine subject's PVR
- Collect urine for pregnancy test in women of childbearing potential if the subject is continuing in the study or collect blood for the pregnancy test if this is the ET Visit
- Draw blood for haematology and biochemistry tests
- Perform 12-lead ECG
- Collect unused study drug and perform drug accountability
- Dispense study drug for the 1-week tapering period (half of the dose to which the subject is randomized)
- Review and collect bladder diary
- Query for AEs including adverse events of special psychiatric interest

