8.7 Safety Endpoints and Analyses

8.7.1 Safety Endpoints

- Incidence and severity of AEs and Adverse Events of interest (urinary retention, withdrawal symptoms) over the course of the study.
- Adverse Events of special psychiatry interest (nervousness, anxiety, panic attacks, insomnia, aggression, mania, suicidal ideation, development/worsening of depression) over the course of the study
- Suicidal Adverse Events and Adverse Events suggestive of abuse potential will be analysed, and detailed narratives provided
- Haematology, chemistry, and urinalysis
- Actual change from end of the Screening Placebo Run-In Period in ECG readings and Week 8. ECG parameters of interest include: ventricular rate, QT interval, corrected QT interval, PR interval, and QRS duration
- Actual change from end of the Placebo Run-In Period to each visit in standardised cuff systolic and diastolic blood pressure and radial heart rate

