1.4 Statistical Analysis Plan Summary (SAP)

This Statistical Analysis Plan (SAP) describes the statistical analysis for the IXA-CSP-002 study. The SAP provides full details of the analyses, the data displays and the algorithms to be used for data derivations. The analysis will be done using the statistical software SAS version 9.4 or higher.

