5.3 Safety variables

All safety variables will be derived from the eCRF.

Adverse Event (AE) An AE is defined as any untoward medical occurrence in a patient or clinical investigation subject administered a pharmaceutical product and which does not necessarily have a causal relationship with this treatment.

Non-Treatment-Emergent Adverse Event (non-TEAE)

When an AE occurs after written consent has been obtained but before the first dose of treatment study drug (Visit 2 date), the AE will be considered a non-treatment emergent AE. Adverse Events, related to abnormal laboratory parameters, that were identified at Visit 2, when blood samples were collected before the first dose of the study drug, are considered non- TEAEs.

Treatment-Emergent Adverse Event (TEAE)

An AE that occurs from the time the subject receives his first dose of treatment study drug (Visit 2 date) until his last study visit (Follow-up Visit date) will be considered a treatment-emergent AE (TEAE) regardless of the assessed relationship to the administration of the study drug.

Immediately Reportable Adverse Event (IRAE)

Immediately reportable AEs (IRAEs) are AEs that must be reported to the Sponsor within 24 hours of the study site being informed of the IRAE.

Immediately reportable AEs include:

- All SAEs
- Overdose
- Pregnancy
- AEs that result in a subject's withdrawal from the study

For litoxetine in the current study and with the current posology, an overdose should be considered as any dose above 60 mg taken per day.

Serious Adverse Event (SAE)

A serious adverse event (SAE) is any untoward medical occurrence or effect that at any dose:

- Results in death
- Is life threatening
- Requires hospitalisation or prolongation of existing hospitalisation
- Results in persistent or significant disability or incapacity
- Is a congenital anomaly or birth defect
- Is another medically important condition

An important medical event that is not immediately life-threatening or will result in death or hospitalisation, but which may jeopardize the subject or may require medical intervention to prevent 1 of the outcomes listed above, should be reported as "serious" as well.

Adverse Event of Special Interest (AESI)

Adverse events of special interest are:

1. Adverse Events of Interest include urinary retention and withdrawal symptoms.

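### Post-void residual volume is scanned at baseline and at the end of treatment, but neither document plans to report it, so urinary retention would be judged from recorded adverse events alone

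*Protocol*

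**What the plan says.** **Collection.** Protocol 6.1.8 states that "Bladder scans (ultrasound) for postvoid residual volume will be recorded at the time points outlined on the Schedule of Assessments". It asks for the scan within 15 minutes of the void and for both times to be recorded. The visit lists in Protocol 7.1.1, 7.1.2 and 7.1.6, and both schedules (Protocol Appendix 2, SAP Figure 1), place PVR at Visits 1, 2 and 6. At Visit 6, which is also the early-termination visit, the instruction is "Determine subject's PVR". SAP 5.5 makes Visit 2 the baseline for all safety variables.

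**Stated use.** Exclusion criterion 12 is "Postvoid residual (PVR) urine volume > 150 mL". Protocol 6.1.8 adds a repeat scan for a high value and then says "If the PVR is >150 mL, the subject will be ineligible for study". Neither document gives any other use.

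**Urinary retention.** The first safety endpoint in Protocol 8.7.1 is "Incidence and severity of AEs and Adverse Events of interest (urinary retention, withdrawal symptoms) over the course of the study", and SAP 2.3 repeats it as the first primary endpoint. SAP 5.3 says that "Adverse Events of Interest include urinary retention and withdrawal symptoms". SAP 6.7 and 6.8 analyse these as adverse events, by system organ class and preferred term, with Clopper-Pearson intervals under 6.7.

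**Completeness.** SAP 1.4 states: "The SAP provides full details of the analyses, the data displays and the algorithms to be used for data derivations".

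**The concern.** Safety and tolerability are the primary objective. Both background sections say that in animals litoxetine raises urethral sphincter pressure and relaxes the detrusor. Incomplete emptying is therefore a foreseeable consequence of the mechanism, and retention is duly named as an event of interest.

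PVR is the only scheduled quantitative measure of bladder emptying. The physical examination covers the urinary system but does not measure residual volume. Eligibility cannot be the reason for the Visit 6 scan, because it was settled eight weeks earlier. Yet under the plan as written, a litoxetine subject could finish treatment with a clearly raised PVR and, unless the investigator chose to record an adverse event, appear in no planned output.

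**Working it through.** No stated figure is in dispute. The check has two parts: whether an analysis of PVR exists anywhere, and how much the retention event count can say without it.

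**1. Where PVR appears**

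| Place | PVR present? |
|---|---|
| Protocol 4.2, 6.1.8 | Yes: eligibility rule and method of measurement |
| Protocol 7.1.1, 7.1.2, 7.1.6, Appendix 2 | Yes: collection at Visits 1, 2, 6 |
| Protocol 8.7.1 (safety endpoints), 8.7.2 (safety analyses) | No |
| SAP abbreviations, Figure 1 | Yes: abbreviation and copied schedule only |
| SAP 1.5 (clarifications from protocol) | No |
| SAP 2.3 (primary endpoints), 5.3 (safety variables) | No |
| SAP 6.7, 6.8 (safety analyses) | No |

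Two readings that might rescue the plan fail. SAP 6.3 promises descriptive statistics for variables in the summary tables, but PVR is assigned to no table. Nor can a listing be assumed: SAP 6.7 names the variables that are to be listed only (pregnancy tests and urinalysis), and PVR is not among them.

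**2. What event counts alone can show**

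Inputs: 78 randomised 2:1, so litoxetine 78 × 2/3 = 52 and placebo 26; the plan's 60 evaluable subjects, so 40 and 20 (Protocol 8.10, SAP 3.1).

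The two-sided Clopper-Pearson 95% upper limit for 0 events in n subjects is 1 − 0.025^(1/n):
- n = 52: 1 − 0.025^(1/52) = 6.8%
- n = 40: 1 − 0.025^(1/40) = 8.8%

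The chance of seeing at least one event in 52 subjects is 1 − (1 − p)^52. The documents give no retention rate, so p is an assumption shown over a range:
- p = 1%: 41%
- p = 2%: 65%
- p = 5%: 93%

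**3. What a PVR comparison would offer**

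The documents give no standard deviation for PVR change, so the precision can be stated only in SD units. The 95% half-width for the arm difference in mean change is 1.96 × √(1/n₁ + 1/n₂) × SD:
- 52 vs 26: 1.96 × √(1/52 + 1/26) = 0.47 SD
- 40 vs 20: 1.96 × √(1/40 + 1/20) = 0.54 SD

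**The case against.** The strongest reply is that retention is not left to chance reporting. Protocol 6.1.2.3 says "Adverse event data should be obtained through observation of the subject, from any information volunteered by the subject, or through subject questioning", and adverse events are queried at Visits 2 to 7. An adverse change on physical examination goes onto the adverse event form (6.1.6), and the event definition in 6.1.2.1 covers unfavourable signs. A raised Visit 6 PVR could therefore be recorded as an event and tabulated. This stands, and a reader who inferred that retention rests only on spontaneous reports would be wrong. It does not close the gap: no threshold or rule says when a raised PVR becomes an event, so recording depends on each investigator.

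Other parts of the reply also limit the point:
- The data are not thrown away. The Visit 1 and Visit 2 values serve eligibility, and the Visit 6 value is recorded. What lacks a planned display is the Visit 6 value and the change from Visit 2.
- PVR is not the only unreported safety measure. Weight is taken at Visits 6 and 7, and the SAP summarises it only among the screening characteristics (6.5).
- The SAP does not depart from a protocol endpoint, because the protocol's own endpoint and analysis lists also omit PVR. SAP 6.7 further classes events of interest as secondary safety analysis.
- The 150 mL limit is an entry criterion with a repeat-scan step. No repeat is specified at Visit 6, and neither document makes 150 mL an on-treatment limit, so a Visit 6 count is descriptive only.
- Scans under the Visit 6 label mix Week 8 with early termination, hence different durations and doses. With 30% dropout assumed, Week 8 pairs will be fewer than the numbers randomised.

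**Conclusion.** The point holds as an omission from the planned reporting. PVR is a protocol safety parameter with a baseline and an end-of-treatment value, and no summary, change or listing is specified in either document. Retention would be assessed only from investigator-recorded events (observed, volunteered or elicited). Zero events among 52 litoxetine subjects would still be compatible with a true rate of up to 6.8%, or 8.8% among 40. These limits assume the planned allocation, and the 40 assumes that the plan's 60 evaluable subjects split 2:1.

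A reader might infer that a PVR comparison would reveal a drug effect that event counts miss. The documents do not support that: they give neither a standard deviation nor an expected shift, and the interval half-width would be about 0.47 to 0.54 SD, so a shift much smaller than half an SD could not be separated from none. The case for the table is that it reports the relevant measurement with its uncertainty.

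The omission biases no planned estimate and changes no test. It is worth correcting because safety is the primary objective and the data are already collected.

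**What to change.** Add PVR to the safety variables in SAP 5.3 and to the analyses in SAP 6.8, for the Safety Population and by arm:

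1. PVR at Visits 2 and 6 and the change from Visit 2, with the mean or median difference between arms and its 95% CI.
2. Number and percent above 150 mL at Visit 6, with Clopper-Pearson 95% CI. State that 150 mL is a descriptive reporting cut-off borrowed from the eligibility rule, and that no repeat scan is specified at Visit 6.
3. Early-termination scans identified separately from Week 8 scans.
4. A subject listing of PVR.

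The text should also be reconciled on timing: Protocol 6.1.8 refers to a scan at Day 0 (Visit 3), whereas the schedule puts Visit 3 at Day 21 with no PVR.

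The cost is one table and one listing from data already collected. No visit, procedure or clinical rule changes. The addition is best made before unblinding.
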